The primary outcome is the count of patients who received the composite outcome of any of the following: naloxone dispensing [prescription, free kit from clinic, or order for home kit], medication assisted treatment [buprenorphine, methadone, naltrexone, acamprosate, gabapentin, disulfiram], addiction consult, referral to outpatient treatment, brief intervention/motivational interviewing for substance misuse. Each component will be indicated separately in the flowsheet for the encounter, along with the type of SUIT team involvement: formal consultation, curbside consultation, or supporting other service. The design is an interrupted time-series prospective observational study. [Time Frame: 30 months]

The secondary outcome is all-cause re-hospitalizations following 6-months from the Index hospital encounter. We will compare healthcare utilization outcomes in all patients between manual screen period and automated screen period controlling for all patient demographic and clinical characteristics. [Time Frame: 24 months of evaluation with 6 months follow-up for rehospitalization] Further exploratory outcomes include analyzing each component of the primary outcome separately: naloxone dispensing, medication assisted treatment, addiction consult, referral to outpatient treatment, brief intervention/motivational interviewing for substance misuse.

Analysis Plan:

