ACFs and partial ACFs will be used to determine the orders of autoregression (AR) or moving average (MA) that will correct for the remaining autocorrelation. We hypothesize that the intervention will promote a step change (binary indicator for a level shift when intervention begins) and possibly a ramp effect (variable takes the value of 0 before the intervention and increases by 1 for each month following the beginning of the intervention). Fit statistics (AIC, BIC) and residual analysis (Ljung-Box test for white noise) will be used to identify a parsimonious and appropriate model based on AR/MA orders, differencing assumptions, and parameters for intervention impact (step, pulse, or ramp).

Specific aim 2: The number of hospitalizations in the 6 months following the index encounter will be regressed on time period of index hospitalization (manual screen or automated screen) and patient demographic and clinical characteristics using mixed-effects Poisson regression models. GLMMs with appropriate link and distributions specified will consider other follow-up utilization outcomes (e.g., costs, any encounter).

Power analysis:

A simulation study was designed to examine potential step effects in a non-inferiority design. In 2020, there were 95 ± 10 addiction consults per month and an autocorrelation AR(1) of $\phi=0.4$. Additionally, we performed silent testing of the automated screener in 2020 where it detected ~ 70 additional cases of substance misuse per month that did not receive consults by the usual care approach. We propose that a non-inferiority margin of 15 consults is acceptable and a step effect of 20 is a feasible goal with the implementation of automated screening. Assuming a similar consult rate of 95 ± 10 per month in this study's pre-period (July 2022-June 2023) and $\phi=0.4$, we have 80% power to detect a step effect of +20, resulting in 115 ± 10 consults per month in the post-period (July 2023-June 2024).

Data Elements:

RUSH EHR

The following electronic health record data elements will be included in the data sets used for analysis. Most data will be obtained through direct extraction of EPIC; however, some data may be computed from EHR data and obtained through the Rush Clinical Research Analytics team or transformed from EHR data by the research team (NLP mapped concepts from the text):

- MRN
- Address with Geocoding
- Census Tract Identifiers
- Encounter ID and type

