- Date / time Stamps for all EHR data (e.g. admission / discharge, procedures, assessments, notes, etc. (time-shifted for final analysis))
- De-identified concept unique identifiers (CUIs) from all clinical documentation in the EHR (process described below)
- Nursing assessments and flowsheets including AUDIT, DAST, and universal screens
- Clinical / nursing assessments, flowsheets, documentation including SUIT data
- Insurance status
- Vital signs (including respirator settings and data)
- Co-morbidities
- ICD and CPT codes

- Cost, charges and reimbursement data associated with all the CPT, ICD9/10, and medications
- patient location
- laboratory results
- radiological orders
- interventional orders including addiction consult orders
- diagnostic test orders
- medication ordered and administered
- sex
- age
- race / ethnicity
- primary and secondary diagnoses
- date of admission
- date of discharge
- dates related to notes, assessments, procedures, orders, reports, vitals, observations, events, diagnoses, etc.
- discharge disposition
- adverse events during hospitalization, defined as Rapid Response Team activations, ICU transfer, cardiac arrest, or mortality
- OR procedures
- OR admission and discharge

DURATION

It is expected that participant enrollment will begin by January 1, 2018 and that human subjects activities will be complete by June 30, 2024. In this pre-post design, a manual screen cohort of patients will provide the comparison. The automated screen period will run prospectively on hospitalized patients over a 12-month period between July 1, 2023 and June 30, 2024. During these study periods, all patient data (for patients ages 18 and above) will be collected.

LOCATION

Research will be conducted at Rush University Medical Center by study staff from Rush. Staff from ITM Loyola and UW-Madison may consult on analyses. All data will be housed at Rush and analyzed on our systems. PHI will not be released outside of Rush.

TYPE AND NUMBER OF SUBJECTS

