A data safety monitoring board has been established to ensure that the data remain confidential and that the participants are not experiencing any harm from the intervention. A committee to ensure that the plan is followed will be formed. The committee will meet every three to six months during the 24-month study period. Members of the data safety monitoring board will include individuals who have demonstrated expertise in the areas related to the project and have agreed to serve in this capacity. [name], is a Professor and Chair of Public Health Sciences in the School of Medicine at Loyola University Chicago and will serve as the Chair of the Data Safety Monitoring Board (letter of support). He has extensive experience in clinical trials and has extensive experience in health inequities research. He has conducted numerous clinical studies and has more than 20 years of NIH funding. [name], MD, is an Associate Professor at Indiana University and a practicing Hepatologist with several NIH/NIAAA-funded grants examining patients with alcoholic hepatitis. He has performed multiple clinical studies in hospitalized patients and involved in clinical trials for alcohol hepatitis treatment. [name], MD, is an Associate Professor at University of Colorado and a critical care physician and currently the PI of a NIAAA R24 multi-site collaboration collecting patient samples for alcohol research. She is familiar with the potential harms in performing alcohol research in hospitalized patients. Finally, [name], PhD, is a Professor of Biostatistics at University of California San Diego and has served on data safety monitoring boards for clinical trials and will help to evaluate the statistical analyses and reports provided by the study team. Of note, the study team will provide the proportion screened and identified to have substance misuse as one of the important metrics to determine any harm that is being incurred in patients missed for SBIRT by the substance misuse NLP classifier.

The Progress of Study and Safety of Patients:

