The following data will be examined to evaluate safety issues: adverse events and rates of adherence to Screening, Brief Intervention, and Referral to Treatment (SBIRT) at all contact points. In order to provide a level of protection to all patients, the following will be specifically included for monitoring and follow-up: (1) number (if any) of patients who were identified by the care team to have substance misuse but was not captured by the automated screener; (2) number (if any) of patients who received screening but refused any intervention; (3) number (if any) of patients who began medication or were referred for treatment; (4) number (if any) who had withdrawal syndrome. Of note, the risks involved with this study are considered low and the manual screen in the control group is an approved intervention for substance misuse by the United States Preventive Services Task Force (USPSTF), the National Institute of Drug Abuse (NIDA), the Center for Disease Control and Prevention (CDC), and the Substance Abuse and Mental Health Service Administration.

- (1) *Compliance with the reporting of adverse events:* Determining whether all adverse events and/or unanticipated problems were reported in writing to Rush University Medical Center and the IRB within 48 hours of discover of the incident. Priority of the DSMB is to analyze presence of any level of harm to patients.
- (2) *Data Accuracy and Protocol Compliance:* Evaluating records for the training of personnel and other protocol documents as needed. All research staff personnel will be required to have human subjects training, HIPPA training, and training on all study protocols. Drs. [name] and [name] will have weekly lab meetings with the project staff and co-investigators. The Substance Use Intervention Team have already been trained for SBIRT and addiction counseling in their practice of usual care currently in place at Rush. At baseline and every six months thereafter, the following will be done by [name], [name], and the staff to ensure compliance: (1) reviewing study documents; (2) auditing the data collection forms for missing data and reasons for missing data; (3) performing analyses of the performance of the substance misuse classifier to ensure no major deviance and harm is occurring. Priorities of the DSMB are to ensure the accurate reporting of the safety data including: 1) manual and automated screening estimates; 2) screen fails; 3) missing data.

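### Aim 2 does not say how death or shortened follow-up enters the 6-month hospitalization count, so a mortality difference between periods would bias the rate ratio, and death is not reported beside it

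*Combined protocol and SAP*

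**What the plan says.** All references are to the combined protocol and SAP.

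- **Study Outcomes:** "The secondary outcome is all-cause re-hospitalizations following 6-months from the Index hospital encounter". The comparison is between periods in all patients, with covariate adjustment.
- **Analysis Plan, Specific aim 2:** "The number of hospitalizations in the 6 months following the index encounter will be regressed on time period of index hospitalization" and on "patient demographic and clinical characteristics using mixed-effects Poisson regression models". Costs and any encounter are named as further follow-up outcomes; death is not. Nothing is said about an offset, censoring, competing risks, or patients who die before discharge.
- **Eligibility criteria:** the only exclusion is inability to take part in the usual-care intervention. Index-stay deaths are not excluded.
- **Data Elements:** the list includes discharge disposition and "adverse events during hospitalization, defined as Rapid Response Team activations, ICU transfer, cardiac arrest, or mortality". No post-discharge date of death is listed.
- **The Progress of Study and Safety of Patients:** the safety data are "adverse events and rates of adherence to Screening, Brief Intervention, and Referral to Treatment (SBIRT) at all contact points". Four items then follow: cases missed by the screener, refusals, treatment starts or referrals, and "number (if any) who had withdrawal syndrome". None of the four is a post-discharge outcome.
- **Safety Monitoring:** "The committee will meet every three to six months during the 24-month study period". The Overview under Methods and Material gives 30 months in total, the last 6 being follow-up.
- **Duration:** the automated period ends on June 30, 2024, and human subjects activities are to be complete by the same date.

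**The concern.** A hospitalization count over a fixed calendar window treats everyone as at risk for the full 6 months. A patient who dies in the index stay cannot be readmitted and, unless excluded, contributes zero, the most favourable value. A patient who dies later keeps any admissions before death but adds no more. If mortality differs between the two periods for any reason, including case mix or secular change in a pre-post design, the Poisson ratio mixes readmission rate with survival. Adjusting for baseline characteristics does not supply the missing time at risk.

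The direction matters because the protocol names patients missed by the classifier as its potential harm. Excess deaths among them would lower the planned count, and deaths outside hospital are not named in any planned output that could reveal this. The same missing offset leaves the analysis exposed if follow-up is cut short for the automated period only.

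**Working it through.** The documents give no death risk, readmission rate, sample size or power for this outcome, so there is no stated figure to reproduce. The study length does reproduce: 12 + 12 + 6 = 30 months. The plan's 80% power concerns monthly consults and plays no part here.

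**1. Bias from deaths.** Let m1 and m2 be the 6-month death risks in the manual and automated periods, counted from the index stay. Let f be the average fraction of the window lost by a patient who dies: f = 1 for index-stay or immediate deaths, f = 0.5 for deaths spread evenly over 6 months. If the readmission rate while alive is equal in both periods, the count ratio without an offset is

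(1 − m2·f) / (1 − m1·f).

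The true ratio is 1.00. With assumed baseline risks and a doubling in the automated period:

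| m1 → m2 | f = 0.5 | f = 1 |
|---|---|---|
| 1% → 2% | 0.990/0.995 = 0.995 | 0.98/0.99 = 0.990 |
| 2% → 4% | 0.98/0.99 = 0.990 | 0.96/0.98 = 0.980 |
| 5% → 10% | 0.95/0.975 = 0.974 | 0.90/0.95 = 0.947 |
| 10% → 20% | 0.90/0.95 = 0.947 | 0.80/0.90 = 0.889 |

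With a risk only 1.25 times higher and f = 0.5, the ratios are 0.999, 0.997, 0.994 and 0.987.

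**2. Is that enough to mislead?** Type and Number of Subjects anticipates about 57,800 patients; an equal split (assumed) gives 28,900 per period. With λ readmissions per patient, the Poisson SE of the log ratio is √(2/(28,900·λ)). At an assumed λ = 0.4 this is √(2/11,560) = 0.0132, so z = −1.96 needs a ratio of exp(−1.96 × 0.0132) = 0.9745, or 0.964 if overdispersion doubles the variance. For λ = 0.2 and 0.8 the thresholds are 0.964 and 0.982 (0.950 and 0.9745 with doubled variance). A doubling from 2% falls short at λ = 0.4. It would cross only with early deaths and λ near 0.8 without overdispersion. A doubling from 5% reaches the λ = 0.4 threshold, and passes it clearly if deaths are early.

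**3. Effect of an offset.** With log time alive and observed as an offset, the ratio returns to 1.00 in every row of the table. The offset does not show the deaths, so death still needs its own line.

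**4. Bias from truncated follow-up.** Under Duration, the automated period and human subjects activities end on the same day. With even accrual (assumed), patients admitted in the first half of the automated year have 6 months observed. Those in the second half have 3 on average. The mean is (6 + 3)/2 = 4.5 months, and 4.5/6 = 0.75. The manual period loses nothing. A count without an offset would then show a ratio near 0.75 with no true effect, well beyond anything in the table.

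**5. Monitoring span.** By the same arithmetic, half of automated-period patients have not completed 6 months at month 24, and 25% of that period's follow-up time falls after the scheduled DSMB meetings; for the manual period the share is 0%.

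**The case against.** The strongest reply is that follow-up is not ignored. Six-month all-cause rehospitalization is the secondary outcome, in-hospital mortality and discharge disposition are collected, and a death during a readmission to the study hospital fits the same data element. The in-hospital limit sits in a list of data elements. The safety section reviews adverse events without repeating that limit and makes any level of harm a DSMB priority. All of this stands. A reader might infer that harm after discharge goes unwatched; the documents do not support that. The gap is narrower: deaths outside hospital, and the absence of any post-discharge outcome among the four listed monitoring items.

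A reader might also infer that every death is scored as zero and that fatal harm would read as benefit. The plan does not say how deaths are scored. Zero follows from the written model only for index-stay deaths that are not excluded. Non-fatal harm, or readmission before death, raises the count, so the net direction under real harm is not fixed. Nor can a number of unseen deaths be derived: the documents give no death risk, and the named harm falls on missed patients, a minority of those with misuse if sensitivity exceeds 80% as the Scientific Review section reports.

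Finally, a DSMB meeting after month 24 would come when the automated period is over and could not protect its patients by stopping the tool. That is fair, and such a meeting is a matter of preference. None of these replies supplies the missing rule for death and time at risk.

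**Conclusion.** The concern holds as an omission in the aim 2 analysis. A fixed-window count with no offset, no restriction to patients discharged alive and no mortality outcome beside it is biased by any between-period difference in mortality. Excess deaths in the automated period push it towards apparent benefit. The size is about 1–2% for a doubling of an assumed 2% risk, 3–5% for a doubling from 5%, and more if deaths are frequent, early or concentrated in frequent readmitters. In most of these scenarios that alone would not produce a significant result.

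The end-date conflict matters more for the same model (ratio near 0.75), but only if data collection really stops on June 30, 2024. The documents do not settle this, since the Overview adds 6 months of follow-up.

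These sizes rest on assumed death risks and readmission rates, an equal split of 57,800, even accrual and equal readmission rates while alive. The primary outcome is not affected by post-discharge death. The change should be made before the aim 2 analysis, but it does not threaten the main comparison.

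**What to change.** - **Aim 2 population and window:** define the population as patients discharged alive, with the 6-month window starting at discharge. The present wording already points to time after the index encounter; make it explicit.
- **Model:** add a log offset for days alive and observed in the window.
- **Companion outcomes:** report death, and rehospitalization-or-death, by period beside the count. Report index-stay deaths by period as well, since they leave the aim 2 population.
- **Data:** add the EHR-recorded date of death to Data Elements, and state that deaths outside the health system are incompletely captured. Settle this early, because identifiers are to be destroyed as soon as the study is complete.
- **Monitoring:** add 30-day and 6-month rehospitalization and recorded death by period to the tabulations given to the DSMB. A further meeting after follow-up ends is optional.
- **Dates:** reconcile the June 30, 2024 end of human subjects activities under Duration with the 6 months of follow-up in the Overview.

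The cost is analysis-plan wording, one added data element and a little more analysis and tabulation. The main downside is incomplete capture of out-of-system deaths. The offset removes the time-at-risk bias only to the extent that deaths are recorded.

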In this study, the aim is to prospectively implement our NLP substance misuse classifier to examine its effectiveness in augmenting current practice that features physician referrals in hospitalized adult patients at Rush University Medical Center (RUMC).

STAFF

All work involving patient data will be performed at Rush and Rush staff will gain access to the Rush servers with approved credentialing and authentication by Rush IT. No data will be accessible to external investigators without a fully executed data use agreement and/or IRB approval / SMART IRB reliance agreement.

TRIAL SETTING AND PARTICIPANTS

This pragmatic, quasi-experimental (pre-post) study will be implemented at Rush University Medical Center across the surgical and medical wards. The study will target all adult hospitalized patients over a 24-month period (12 months of manual screen and 12 months under implementation of the NLP tool) and an additional 6-month follow-up for secondary outcomes. Currently, SUIT performs screening for patients identified from physician referrals between 8am-6pm and Monday-Friday and uses Epic (Epic Systems Corporation, Verona, Wisconsin) EHR.

METHODS AND MATERIAL

Overview:

We will use a quasi-experimental, interrupted time series (ITS) design to evaluate the longitudinal effects of the automated screening classifier compared to the manual screen approach at Rush. ITS offers several advantages in making use of our longitudinal data. Our analysis will model the trend in the outcome before the implementation of the automated screen, the change in the outcome that can be attributed to the automated screen and the difference between the slopes in the pre-period versus post-period. It is anticipated that no other interventions that may impact the study outcome will occur during the study period.

A comparison cohort from the manual screen period will extend from August 1, 2022 to July 31st, 2024. The day of switching on the automated screen will mark the start of the intervention period on August 1, 2023 and extend through July 31, 2024. This provides a 30-month total study period (12 months manual screening, and 12 months automated screen, and 6 months additional follow-up for secondary outcomes).

Approach:

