Overall approach: Demographic and clinical characteristics between the manual and automated screen periods will be examined using bivariate statistics. We will also perform descriptive analysis to examine the proportion of hospitalized patients with substance misuse who received any component of the composite outcome (naloxone dispensing, medication-assisted treatment, addiction consult, referral to outpatient treatment, brief intervention/motivational interviewing for substance misuse) within each month of the study period, and we will plot these proportions using mixed-effects logistic regression, with time (month of observation) modeled using restricted cubic splines. The primary analysis for aim 1 will consist of an interrupted time series approach utilizing autoregressive integrated moving average (ARIMA) models to determine the effect of the automated screener to the manual screen for this outcome. ARIMA models are preferable to alternatives such as segmented regression which may inadequately control for seasonality and autocorrelation in time series data. We will also perform sensitivity analyses to confirm the results of aim 1 using generalized linear mixed-effects models (GLMM) that include random intercepts to account for multiple index encounters over the follow-up time period and adjust for important patient demographics and clinical characteristics including: age, sex, race/ethnicity, insurance status, diagnosis, and comorbidities. GLMMs will also be used to analyze secondary endpoints.

Specific aim 1: First, we will plot the counts of hospitalized patients who received any component of the composite outcome to examine seasonality, trends, and outlying values. A transformation will be applied to stabilize the variance over time if data are heteroscedastic. Differencing will be applied to induce stationarity, such as a difference to account for linear trend ($d=1$, degree of non-seasonal differencing) and autocorrelation functions (ACF) will be plotted to verify stationarity. After differencing,

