EHR data for adult (ages 18 and above) patients will be collected. The target study population is adult (ages 18 and above)- male or female – that were identified by the manual or automated screening for substance misuse at Rush University Medical Center. Additionally, patients meeting only the age criteria within the specified time-frame for the study may be included for analyses regardless of potential of or screening for substance misuse. Investigators at Rush University anticipate approximately 57,800 RUMC patients will be included in the analysis, based on preparatory research planning.

POTENTIAL RISKS & BENEFITS

The main risk to subjects is breach of confidentiality. All data is maintained electronically and stored on password-protected computers using secured servers with limited access maintained at Rush University Medical Center. For analysis, Rush will access a delimited file containing patient notes and then process the data, load the model, and make a prediction for each patient. The software will generate output in the

form of a delimited file linking each patient's unique identifier (such as MRN) to a prediction about the patient's alcohol, opioid, non-opioid, and polysubstance use statuses. All these activities will be performed locally within Rush's HIPAA-secure servers.

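### The aim 2 model for 6-month rehospitalization names no calendar-time term or month-level variance, so its period contrast should be reported as an uncontrolled before-after association with a trend-adjusted check beside it

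*Combined protocol and SAP*

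**What the plan says.** Methods and Material, Overview, sets the design as an interrupted time series: "Our analysis will model the trend in the outcome before the implementation of the automated screen", followed by the change at implementation and the difference between the two slopes.

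The Analysis Plan carries this through for the composite outcome only. Aim 1 uses ARIMA, chosen over "segmented regression which may inadequately control for seasonality and autocorrelation in time series data", and expects that "the intervention will promote a step change (binary indicator for a level shift when intervention begins) and possibly a ramp effect". The month splines under Overall approach serve a descriptive plot of the composite.

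For rehospitalization, Study Outcomes says "We will compare healthcare utilization outcomes in all patients between manual screen period and automated screen period", controlling for patient characteristics. Specific aim 2 fits a mixed-effects Poisson model in which the count "will be regressed on time period of index hospitalization (manual screen or automated screen) and patient demographic and clinical characteristics". No month, trend, slope-change or seasonal term is named.

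The only random effect in the plan is an intercept for patients with several index encounters. It is described for the aim 1 sensitivity models, and the same paragraph ends with "GLMMs will also be used to analyze secondary endpoints".

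**The concern.** A two-level period indicator compares the average of one year with the average of the next. Case-mix adjustment removes only the change that runs through measured patient characteristics. Whatever else moves readmission from one year to the next enters the period coefficient and would be read as a difference between screening methods. The plan models time for aim 1 to guard against this, and aim 2 does not have the same protection.

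A second, smaller matter is variance. A patient-level intercept does not capture shocks shared by everyone admitted in the same month. If such shocks exist, the standard error of the period coefficient is too small, although the coefficient itself is not biased.

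**Working it through.** The plan gives no sample size, power or expected rate for aim 2, so there is no figure of its own to reproduce.

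**Inputs from the documents.** Two 12-month periods (Trial Setting and Participants); 6-month follow-up; "approximately 57,800 RUMC patients will be included in the analysis" (Type and Number of Subjects).

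**Assumptions.** All 57,800 fall evenly in the 24 months, so n = 28,900 per period; 0.3 rehospitalizations per patient in 6 months; dispersion 1, 2 or 3; two-sided 5% test. Drift g is what remains after covariate adjustment.

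**Bias.** The period midpoints are 12 months apart, so the period log rate ratio is shifted by 12g, whatever the sample size. A drift of 3% per year gives ln(1.03) = 0.0296; 5% gives ln(1.05) = 0.0488.

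**Standard error of the period contrast.** SE = sqrt(2 × dispersion / (n × rate)). With n × rate = 8,670, SE = 0.0152, 0.0215 and 0.0263 for dispersion 1, 2 and 3.

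**False positives with no screener effect** (normal approximation):

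| Yearly drift | Dispersion 1 | Dispersion 2 | Dispersion 3 |
|---|---|---|---|
| 3% | 49% | 28% | 20% |
| 5% | 89% | 62% | 46% |

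The Duration section mentions enrolment from January 2018. If the 57,800 were spread over the 78 months to June 2024, n would be 57,800 × 12/78 = 8,892 per period, SE 0.0274 to 0.0474, and 3% yearly drift would give about 10% to 19%.

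**Season.** Both periods cover the same 12 calendar months, so a stable annual cycle contributes zero to the period contrast. It does not cancel once a linear month term is added: without seasonal terms, the level change is biased by up to 1.945 times the seasonal amplitude. With one sine/cosine pair, the bias for a single annual sinusoid is zero.

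**Month-level variance.** With no drift and an assumed month SD of 2%, true SE = sqrt(SE² + 2 × 0.02²/12) = 0.0172, 0.0230 and 0.0275. A test that uses the model SE then rejects 8%, 7% and 6% of the time.

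**Price of adjustment.** Over 24 equal months with period, month, period-by-month and one sine/cosine pair, the SE relative to the period contrast is ×3.01 for the level change and ×3.48 for the average post-period difference. The 95% half-width, exp(1.96 × multiplier × SE) − 1, at dispersion 1 to 3 is:

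- period contrast: 3.0% to 5.3%
- level change: 9.4% to 16.8%
- average post-period difference: 10.9% to 19.6%

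**Follow-up overlap.** Follow-up lasts 6 months, so index admissions in the last six manual-screen months have outcome windows that run past switch-on. The pre-trend by index month is therefore not wholly pre-intervention.

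**The case against.** The strongest reply is that trend adjustment can be less accurate than the planned contrast, even when drift exists. At 3% yearly drift, the root mean squared error of the period contrast, sqrt(0.0296² + SE²), is 0.033, 0.037 and 0.040 for dispersion 1 to 3. The adjusted level change has SE 0.046, 0.065 and 0.079. At 5% drift the period contrast has 0.051, 0.053 and 0.055, so adjustment wins only at dispersion 1. Drift that is not linear can also mislead the adjusted model: a 5% log-linear rise over the first six months, then flat, biases the period contrast by about +1.4%, the adjusted level by −1.2% to −1.4% and the adjusted average by −3.8%. This stands. A reader might infer that the period model should be replaced, and these figures do not support that.

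The Overview could also be read as covering every outcome, with aim 2 only a short summary. That is possible, but the aim 2 text is specific and omits the terms; if they are intended, writing them in settles the matter. The expectation that no other interventions will occur does not remove drift, and aim 1 models trend under the same expectation.

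Two further inferences fail. One is that aim 2 has no stated random effect at all: the Overall approach paragraph can fairly be read as giving it the patient-level intercept, and only a month-level component is missing. The other is that aim 2 is confined to patients "identified by the manual or automated screening for substance misuse at Rush University Medical Center", since that is how the target population is described. Study Outcomes specifies all patients for utilization outcomes, and the same section on subjects allows patients to be included regardless of screening.

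**Conclusion.** The gap in the text is real: aim 2 as written has no calendar term, and residual log-linear drift passes in full, as 12g, into the period coefficient. That result needs no assumed rate or sample size. The false-positive figures do need them: about 20% to 49% at 3% yearly drift rests on assumed drift, rate and dispersion and on an even 24-month split. The month-variance effect is small at the assumed SD of 2%.

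A reader might infer that aim 2 will be biased. The documents do not show this: they give no drift, and seasonality alone does no harm to the period contrast. The outcome is secondary and has no power statement. The point is one to consider. It bears mainly on what aim 2 may claim.

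**What to change.** Add to Specific aim 2:

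1. Keep the period-only contrast, with a month-level standard error and a small-sample t reference (24 months). Label it an uncontrolled before-after association that is not attributed to the screener.
2. Beside it, report a sensitivity model with index month centred at switch-on, a period-by-month slope and one annual sine/cosine pair. Give the level change, slope change and average post-period difference with confidence intervals. Month-of-year indicators cannot be used: over two years they make period and linear month collinear.
3. State that follow-up of the last six manual-screen months crosses switch-on. Add a sensitivity analysis that excludes those months or censors their follow-up at switch-on.
4. Confirm that the true index month is kept for analysis, since Data Elements says time stamps will be shifted.

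No new data are needed. The cost is precision in item 2, as shown above, so those estimates serve only as a check.

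Item 3 also has a price. Excluding six months leaves 6 against 12: the SE of the period contrast rises by sqrt((1/6 + 1/12)/(2/12)) = 1.22, the midpoints move to 15 months apart, and a stable annual cycle no longer cancels. In the item 2 model the multipliers become about ×7 and ×11, so exclusion suits the period contrast only. Censoring keeps all 12 calendar months but needs a person-time offset, and shorter windows are comparable only if the readmission rate is roughly constant over follow-up.
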